### 8.2.2 *Relationship to IP*

The clinician's assessment of an AE's relationship to the IP (i.e. Vivitrol) is part of the documentation process, but it is not a factor in determining what is or is not reported in the study. If there is any doubt as to whether a clinical observation is an AE, the event should be reported. All AEs must have their relationship to study agent assessed. In a clinical trial, the IP must always be suspect. To help assess, the following guidelines are used.

- **Definitely Related** – There is clear evidence to suggest a causal relationship, and other possible contributing factors can be ruled out. The clinical event, including an abnormal laboratory test result, occurs in a plausible time relationship to drug administration and cannot be explained by concurrent disease or other drugs or chemicals. The response to withdrawal of the drug (dechallenge) should be clinically plausible. The event must be pharmacologically or phenomenologically definitive, with use of a satisfactory rechallenge procedure if necessary.
- **Probably Related** – There is evidence to suggest a causal relationship, and the influence of other factors is unlikely. The clinical event, including an abnormal laboratory test result, occurs within a reasonable time after administration of the drug, is unlikely to be attributed to concurrent disease or other drugs or chemicals, and follows a clinically reasonable response on withdrawal (dechallenge). Rechallenge information is not required to fulfil this definition.
- **Possibly Related** – There is some evidence to suggest a causal relationship (e.g., the event occurred within a reasonable time after administration of the trial medication). However, other factors may have contributed to the event (e.g., the participant's clinical condition, other concomitant events). Although an AE may rate only as "possibly related"

soon after discovery, it can be flagged as requiring more information and later be upgraded to “probably related” or “definitely related,” as appropriate.

- **Unlikely to be related** – A clinical event, including an abnormal laboratory test result, whose temporal relationship to drug administration makes a causal relationship improbable (e.g., the event did not occur within a reasonable time after administration of the trial medication) and in which other drugs or chemicals or underlying disease provides plausible explanations (e.g., the participant’s clinical condition, other concomitant treatments).
- **Not Related** – The AE is completely independent of study drug administration, and/or evidence exists that the event is definitely related to another etiology. There must be an alternative, definitive etiology documented by the clinician.

### 8.2.3 *Expectedness*

#### 8.2.3.1 Adverse Events from the use of Vivitrol

Common side effects of Vivitrol may include:

- *sleepiness*
- *headache*
- *dizziness*
- *vomiting*
- *decreased appetite*
- *painful joints*
- *muscle cramps*
- *cold symptoms*
- *trouble sleeping*
- *toothache*

Serious side effects may include:

- *Depressed mood*
- *Pneumonia, symptoms include;*
  - *shortness of breath or wheezing*
  - *coughing that does not go away*
- *Serious allergic reactions, symptoms include;*
  - *skin rash*
  - *swelling of your face, eyes, mouth, or tongue*
  - *trouble breathing or wheezing*
  - *chest pain*
  - *feeling dizzy or faint*

### **8.3 TIME PERIOD AND FREQUENCY FOR EVENT ASSESSMENT AND FOLLOW-UP**

The occurrence of an AE or SAE may come to the attention of study personnel during study visits and interviews of a study participant presenting for medical care, or upon review by a study monitor.

All AEs including local and systemic reactions not meeting the criteria for SAEs will be captured on the appropriate CRF. Information to be collected includes event description, time of onset, clinician's assessment of severity, relationship to study product (assessed only by those with the training and authority to make a diagnosis), and time of resolution/stabilization of the event. All AEs occurring while on study must be documented appropriately regardless of relationship. All AEs will be followed to adequate resolution.

Any medical condition that is present at the time that the participant is screened will be considered as baseline and not reported as an AE. However, if the study participant's condition deteriorates at any time during the study, it will be recorded as an AE.

Changes in the severity of an AE will be documented to allow an assessment of the duration of the event at each level of severity to be performed. AEs characterized as intermittent require documentation of onset and duration of each episode.

The PI will record all reportable events (as defined in 8.4) with start dates occurring any time after informed consent is obtained until 7 (for non-serious AEs) or 30 days (for SAEs) after the last day of study participation. At each study visit, the investigator will inquire about the occurrence of AE/SAEs since the last visit. Events will be followed for outcome information until resolution or stabilization.

In the event of study discontinuation for any reason, any ongoing AEs will be followed until resolution or until deemed stable by the PI, or until the participant is deemed by the PI to be lost to follow-up. If, in the opinion of the PI, it is necessary to monitor a participant beyond the safety follow-up visit, the follow-up period may be extended as necessary. In such instances, the Sponsor and the PI will agree to an acceptable follow-up schedule. The PI must maintain a record of all participants who fail to complete the study. The reason for study discontinuation will be made on the appropriate CRF.

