### 2.1.4 *Investigational Product: Vivitrol IM 380 mg*

In 2006, a 30 day NTX intramuscular injection known as Vivitrol (Alkermes) was approved by the FDA for the treatment of alcohol dependence, and it was also approved in 2010 for the treatment of opioid dependence. Vivitrol consists of a NTX PLGA microsphere suspension delivered intramuscularly via an injection. Some studies revealed that a 380 mg injection can produce a mean trough naltrexone blood level above 1.33 ng/ml for approximately four weeks.

Vivitrol PK will be captured in the present study to be used as a reference product in [REDACTED]  
[REDACTED] drug application for the OLANI product which is being developed under [REDACTED]  
[REDACTED]

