#### 1. Vulnerability to Opioid Overdose

After opioid detoxification, patients are likely to have reduced tolerance to opioids. VIVITROL blocks the effects of exogenous opioids for approximately 28 days after

administration. However, as the blockade wanes and eventually dissipates completely, patients who have been treated with VIVITROL may respond to lower doses of opioids than previously used, just as they would have shortly after completing detoxification. This could result in potentially life-threatening opioid intoxication (respiratory compromise or arrest, circulatory collapse, etc.) if the patient uses previously tolerated doses of opioids. Cases of opioid overdose with fatal outcomes have been reported in patients who used opioids at the end of a dosing interval, after missing a scheduled dose, or after discontinuing treatment.

Patients should be alerted that they may be more sensitive to opioids, even at lower doses, after VIVITROL treatment is discontinued, especially at the end of a dosing interval (i.e., near the end of the month that VIVITROL was administered), or after a dose of VIVITROL is missed. It is important that patients inform family members and the people closest to the patient of this increased sensitivity to opioids and the risk of overdose.

There is also the possibility that a patient who is treated with VIVITROL could overcome the opioid blockade effect of VIVITROL. Although VIVITROL is a potent antagonist with a prolonged pharmacological effect, the blockade produced by VIVITROL is surmountable. The plasma concentration of exogenous opioids attained immediately following their acute administration may be sufficient to overcome the competitive receptor blockade. This poses a potential risk to individuals who attempt, on their own, to overcome the blockade by administering large amounts of exogenous opioids. Any attempt by a patient to overcome the antagonism by taking opioids is especially dangerous and may lead to life-threatening opioid intoxication or fatal overdose. Patients should be told of the serious consequences of trying to overcome the opioid blockade.

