## 2. Injection Site Reactions

VIVITROL must be prepared and administered by a healthcare provider. VIVITROL injections may be followed by pain, tenderness, induration, swelling, erythema, bruising, or pruritus; however, in some cases injection site reactions may be very severe. In the clinical trials, one patient developed an area of induration that continued to enlarge after 4 weeks, with subsequent development of necrotic tissue that required surgical excision. In the postmarketing period, additional cases of injection site reaction with features including induration, cellulitis, hematoma, abscess, sterile abscess, and necrosis, have been reported. Some cases required surgical intervention, including debridement of necrotic tissue. Some cases resulted in significant scarring. The reported cases occurred primarily in female patients.

VIVITROL is administered as an intramuscular gluteal injection, and inadvertent subcutaneous injection of VIVITROL may increase the likelihood of severe injection site reactions. The needles provided in the carton are customized needles. VIVITROL must not be injected using any other needle. The needle lengths (either 1 1/2 or 2 inches) may not be adequate in every patient because of body habitus. Body habitus should be assessed prior to each injection for each patient to assure that the proper needle is selected and that the needle length is adequate for intramuscular administration. For patients with a larger amount of subcutaneous tissue overlying the gluteal muscle, the administering healthcare provider may utilize the supplied 2-inch needle with needle protection device to help ensure that the injectate reaches the intramuscular mass. For very lean patients, the 1 1/2-inch needle may be appropriate to prevent the needle contacting the periosteum. Either needle may be used for patients with average body habitus. Healthcare providers should ensure that the VIVITROL injection is given correctly, and should consider alternate treatment for those patients whose body habitus precludes an intramuscular gluteal injection with one of the provided needles.

Patients should be informed that any concerning injection site reactions should be brought to the attention of the healthcare provider. Patients exhibiting signs of abscess, cellulitis, necrosis, or extensive swelling should be evaluated by a physician to determine if referral to a surgeon is warranted.

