#### 5.4.2.1 Participant Monitoring and Removal from Study

The psychiatrist and/or therapist will assess appropriateness for continuation in the research study on a continuous basis and will remove from the trial participants with significant clinical deterioration or noncompliance of a type which could be dangerous. Criteria for removal from the study will include:

1. Clinical deterioration which cannot be managed safely in the context of outpatient treatment. This would include a participant who becomes suicidal, or a participant who goes on drug binges (including non-opiate drugs).
2. Elevation of liver enzymes  $>3$  times normal. The PI or a study physician is available 24 hours/day by phone in case of emergency.

For those who withdraw from the study may request to withdraw from data collection and have no further contact with study site. Participants shall be informed that for a period of time 30 days after their last Vivitrol injection there may a risk that opioid based medication may have a reduced affect. There is no option to remove Vivitrol from a participant.

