#### ***7.3.6 Early Termination Visit***

Any participants that are withdrawn will be requested to attend Clinilabs for an early termination /withdrawal visit as outlined in Table 7-1. Participants will be advised of their option as outlined in section 5.4.2.

A follow-up visit may be conducted 30 days after the last scheduled on-study visit and is required only if a participant has ongoing AEs or laboratory abnormalities at the last on-study visit. An in-clinic follow-up visit must be conducted 30 days after the last scheduled on-study visit for an AE requiring laboratory testing for participants with the following conditions at the last on-study visit: ongoing AEs, SAEs regardless of attributability, any laboratory abnormalities considered to be AEs or potentially harmful to the participant. For in-clinic follow-up visits, assessments performed should reflect what is considered medically necessary to assess the event(s).

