## 7.5 PROHIBITED MEDICATIONS, TREATMENTS AND PROCEDURES

The medications and substances listed below are prohibited for the specified time periods:

- **Buprenorphine**, either as part of a maintenance program or any illicit/non prescribed is prohibited for the duration of the study.
- **Methadone** is prohibited at least 14 days prior to Day 0 and for the duration of the Study.
- All other **opioids** are prohibited for the duration of the study unless approved by the PI or study clinician (see section 7.7)
- **Oral naltrexone** is prohibited for at least 30 days prior to Day 0 and for the duration of the study
- **Extended release naltrexone (e.g., Vivitrol)** is prohibited for at least 60 days prior to Day 0 and for the duration of the study unless administered under this trial protocol.

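### Non-serious AE recording stops 7 days after a participant leaves, so someone who leaves soon after an injection is unobserved for part of the protocol's own 28 to 30 day effect period

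*Combined protocol and SAP*

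**What the plan says.** Section 8.3 has reportable events recorded from consent "until 7 (for non-serious AEs) or 30 days (for SAEs) after the last day of study participation". No section ties the end of AE collection to the last injection.

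Three places say how long an injection acts:

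- Section 2.1.4, on drug level: "a 380 mg injection can produce a mean trough naltrexone blood level above 1.33 ng/ml for approximately four weeks".
- Section 2.3.1, item 1, on effect: "VIVITROL blocks the effects of exogenous opioids for approximately 28 days" after dosing.
- Section 5.4.2.1, on what withdrawing participants are told: "for a period of time 30 days after their last Vivitrol injection there may a risk that opioid based medication may have a reduced affect". The same section adds: "There is no option to remove Vivitrol from a participant".

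Section 7.3.6 asks withdrawn participants to attend an early termination visit but does not time it against the last injection. The later 30-day visit "is required only if a participant has ongoing AEs or laboratory abnormalities at the last on-study visit". Section 7.3.8 and footnote 3 of Table 7-1 set the same condition.

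AE incidence is a secondary endpoint, with injection-site reactions and hepatic effects as AEs of special interest (Sections 3.2 and 4.2.2).

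**The concern.** When Section 5.4.2.1 warns a withdrawing participant, it counts 30 days from the last injection. When Section 8.3 collects that participant's AEs, it counts 7 days from leaving. For a depot that cannot be taken out, these can be far apart: someone may leave a few days after an injection and carry active drug for weeks with no recording of new non-serious events.

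What is at stake is even ascertainment of a secondary safety endpoint. Section 10.4.5 reports the number and percentage of participants with treatment-emergent AEs, and Section 10.4 makes no allowance for unequal follow-up. An early leaver with a truncated window counts in the percentage in the same way as a completer. With 15 participants, one missed case is 1/15, or about 7 percentage points.

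**Working it through.** The plan gives no figure of its own to reproduce, so this is date arithmetic on its stated windows.

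**Inputs**

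- Recording window after leaving: 7 days for non-serious AEs, 30 days for SAEs (Section 8.3).
- Effect period H after an injection: 28 days (Sections 2.1.4 and 2.3.1) or 30 days (Section 5.4.2.1).
- Completer: last injection on Day 140, final visit on Day 196 (Section 7.3.3.4 and Table 7-1).
- Expected completion: 12 of 15 (Section 5.3.1).

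**Formula.** A participant leaves x days after the last injection. Uncovered days are max(0, H − (x + 7)) for non-serious AEs and max(0, H − (x + 30)) for SAEs.

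**Completer.** Non-serious recording closes on Day 196 + 7 = 203, which is 203 − 140 = 63 days after the last injection. SAE recording closes on Day 196 + 30 = 226, which is 86 days after it. There is no gap.

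**Early leaver**

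| Leaves x days after last injection | Non-serious window closes (x + 7) | Uncovered, H = 28 | Uncovered, H = 30 | SAE uncovered, either H |
|---|---|---|---|---|
| 0 | 7 | 21 | 23 | 0 |
| 5 | 12 | 16 | 18 | 0 |
| 7 | 14 | 14 | 16 | 0 |
| 14 | 21 | 7 | 9 | 0 |
| 21 | 28 | 0 | 2 | 0 |
| 23 | 30 | 0 | 0 | 0 |

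The row x = 5 is, for example, a third injection on Day 56 and departure on Day 61. Non-serious recording ends on Day 68, and 68 − 56 = 12 days. SAE recording ends on Day 91, and 91 − 56 = 35 days.

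**How many withdrawals are exposed.** If departures were spread evenly over a 28-day interval (an assumption, not in the plan), 21/28 = 75% (H = 28) to 23/28 = 82% (H = 30) would leave some gap. This may be too high. Table 7-1 has no visit between injections for doses 2 to 5, and a participant who withdraws at the next injection visit is about 28 days past dosing and has no gap.

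**How many people.** Section 5.3.1 implies 15 − 12 = 3 non-completers, but it defines completion by PK samples, including the Day 168 trough. Anyone with a gap has left less than 23 days after an injection. Since the last injection is on Day 140, that is before about Day 163, so such a person is also a PK non-completer. The reverse does not hold: a participant may miss samples and still attend to Day 196. Three is therefore an upper guide.

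**The case against.** The strongest reply is that little is lost. AEs ongoing at discontinuation are followed until resolved or stable (Section 8.3), and Sections 7.3.6 and 7.3.8 require a 30-day visit for them. The SAE window always reaches at least 30 days past the injection. Section 8.1.1 allows AEs to be identified by telephone, the investigator may extend follow-up, and safety is a descriptive endpoint for an approved product. The point at which participation ends is also undefined: someone who stops injections but keeps attending has no gap.

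Most of this stands, and it confines the point to new-onset non-serious AEs in people who leave soon after an injection. It does not close that gap. The telephone and extension provisions are discretionary, the 30-day visit depends on something already being wrong, and no rule captures a new event more than 7 days after departure.

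A reader might infer more in four ways that the documents do not support:

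- **A late severe reaction would go unseen.** Section 2.3.1 reports that "one patient developed an area of induration that continued to enlarge after 4 weeks". That lesion was already present before then. If it existed at withdrawal or began within 7 days, Section 8.3 would have it followed. It does not illustrate a missed new-onset event.
- **People who stop because of an AE are the ones undercounted.** The AE that made them stop is followed. Only further, new events are exposed.
- **The shortfall is 63 − 12 = 51 days.** The 63 days is how long completers happen to be watched, not a stated risk period.
- **SAE collection is also too short.** That needs a horizon of 56 to 60 days. The 56 days is the span from Day 140 to Day 196. The 60 days comes from Section 7.5, where extended-release naltrexone "is prohibited for at least 60 days prior to Day 0". Neither is given as a duration of release or effect.

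**Conclusion.** The point holds within limits. Against the protocol's own 28 to 30 days, a participant who leaves less than about 21 to 23 days after the last injection has an uncollected period for new non-serious AEs. It is at most 21 to 23 days, and 16 to 18 days in the Day 61 example. Completers, later leavers, SAEs and AEs ongoing at withdrawal are not affected.

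This assumes that participation ends when the participant leaves or attends the early termination visit, which the plan does not define, and that the 28 to 30 day figures are a fair minimum for the period of interest. Any bias would be towards too few events, but its size cannot be calculated. With no more than about three people likely to be concerned, this is a cheap improvement, not a flaw that threatens the study's conclusions.

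**What to change.** In Section 8.3, end non-serious AE recording at the later of 7 days after participation ends and 30 days after the last Vivitrol injection. This matches the period that Section 5.4.2.1 already gives to withdrawing participants. The window then closes max(x + 7, 30) days after the injection, so nothing is uncovered at H = 28 or 30 for any x. Completers stay at max(63, 30) = 63 days. The SAE rule need not change.

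In Section 7.3.6, add one telephone contact about 30 days after the last injection, covering AEs and the injection site. It should apply to every early leaver who received an injection and still consents to contact, whether or not an AE is ongoing.

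The cost is protocol wording, one call each for a few participants, and a few more AE records. Some leavers will decline, as Section 5.4.2.1 allows. A call will not detect asymptomatic laboratory changes, so it does not improve ascertainment of silent liver enzyme elevations.

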### **8.4 REPORTING PROCEDURES**

#### ***8.4.1 Adverse Event Reporting***

The Sponsor will inform the investigator of any new information that may impact the conduct of the trial or have an impact on the ethical acceptability of the trial.

Investigator will keep records of all AE's on an ongoing basis. Significant concerns or unexpected AE's from [name] and [name] are to be reviewed by the DSMB via email or conference call. The Sponsor will update the protocol regularly with any new safety information relating to the drug.

#### ***8.4.2 Serious Adverse Event Reporting***

All SAEs should be reported as appropriate to the Sponsor, NYSPI IRB, FDA and Data Safety Monitoring Panel (DSMP) except for those SAEs that the protocol or other document (e.g., Manufacturer's labelling) identifies as not needing expedited reporting. The expedited

reports should be followed promptly by detailed, written reports. The reports should identify participants by unique code numbers assigned to the trial participants rather than by the participants' names personal identification numbers, and/or addresses.

#### **8.4.2.1 Management of SAE's**

SAEs, as defined by the FDA, will be systematically evaluated at each clinic visit. Any SAE, whether or not related to IP, will be reported to the NYSPI IRB and DSMP. The initial SAE report will be followed by submission of a completed SAE report to both institutions. The PI and study monitor will evaluate SAEs and bring them to the attention of the DSMB at the next scheduled meeting or sooner if there are significant concerns.

In the event that a participant either withdraws from the study or the investigator decides to discontinue a participant due to SAE, the participant will have appropriate follow-up medical monitoring. Monitoring will continue until the SAE has resolved or stabilized with no further change expected, is clearly unrelated to IP, or results in death. Outcome of SAEs will be reported to the NYSPI IRB and DSMP as soon as this information becomes available. A summary of the SAEs that occurred during the previous year will be included in the annual progress report to the NYSPI IRB, FDA & DSMP.

